7 ANALYSIS COHORTS

7.1 PK Cohort

7.1.1 Safety Population

The safety population will consist of all subjects and sinuses exposed to the investigational device with successful dilation of at least one FSO. All primary and secondary endpoint analyses will be performed on the safety population for the PK cohort.

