9.2 Study Endpoints

9.2.1 Primary Endpoints

PK cohort: Successful balloon dilation of attempted FSO using the UP Drug-Coated Device with no unanticipated serious adverse device effects (USADE). Successful dilation is defined as insertion of the UP Drug-Coated Device into the targeted FSO followed by 2 consecutive complete inflations of the balloon.

Randomized cohort: Difference in patency grade of the FSO between treatment sides at Day 30 as determined by an independent, blinded sinus surgeon based on the centralized, video-endoscopy review.

- Patency of the FSO is assessed endoscopically by probing with a 3-mm olive-shaped frontal sinus suction tip (“suction tip”) and graded on a 5-point scale.

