16.3 Analysis of Primary Endpoints

PK cohort

The primary efficacy endpoint is the number of successful balloon dilations, which will be reported with descriptive statistics. The left and right sides of each subject will be considered independent, and each subject is expected to contribute up to 2 observations. The study will be considered successful if $\geq 80\%$ of attempted FSO are dilated successfully with no USADE related to the investigation device. A successful FSO dilation is one in which the physician has inserted the UP Drug-Coated Device into the targeted FSO, followed by 2 consecutive, complete inflations of the balloon.

Continuous data from the plasma MF, plasma cortisol and 24-hour urinary cortisol concentrations will be expressed using descriptive statistics, including but not limited to, means, standard deviations, medians, ranges and, where appropriate, coefficient of variation (%).

Randomized cohort

The primary efficacy endpoint is the difference in the patency grade between treatment sides at Day 30 as determined by an independent, blinded sinus surgeon based on the centralized video-endoscopy review.

The primary efficacy endpoint will be analyzed using the paired t-test.

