16.8 Analysis Populations

PK cohort: The PK population will consist of all subjects in the safety population with at least one non-missing and eligible plasma concentration value.

Safety population will consist of all subjects and sinuses exposed to investigational device with successful dilation of at least one FSO.

Randomized cohort: All primary analyses will be conducted on the intent-to-treat population. Additional analyses may be performed on the per-treatment-evaluable population.

- *Intent-to-Treat* (ITT) population will consist of all subjects and sinuses where a sinus dilation was attempted. An attempt occurs when the physician introduces the UP Device into the subject's nostril with the intent of dilation. Subjects and sinuses will be analyzed according to randomization assignment.
- *Per-Treatment-Evaluable* (PTE) population will consist of all randomized patients and sinuses which have received the assigned study device in the target sinus, who have no major procedural protocol deviations, and for whom follow-up data are available.

If a subject decides to discontinue from the study, every attempt will be made to continue to collect the safety and efficacy data according to the protocol procedures.

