6 STUDY ENDPOINTS

6.1 Primary Endpoints

PK Cohort: The primary endpoint in the PK cohort is the successful balloon dilation of attempted FSO using the UP Drug-Coated Device with no unanticipated serious adverse device effects (USADE).

- Successful dilation of the FSO is defined as insertion of the UP Drug-Coated Device into the targeted FSO followed by 2 consecutive complete inflations of the balloon.

Randomized Cohort: The primary efficacy endpoint for the randomized cohort is the difference in the patency grade of the FSO between treatment sides at Day 30, as determined by an independent, blinded sinus surgeon based on the centralized video-endoscopy review.

- Patency of the FSO is assessed endoscopically by probing with a 3-mm olive-shaped frontal sinus suction tip (“suction tip”) and graded on a 5-point scale.

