10.3 Primary Endpoints

10.3.1 PK Cohort – Primary Endpoint

The primary endpoint is the number of successful sinus dilations of all attempted FSO using the UP Drug-Coated Device. The left and right sides of each subject will be considered independent, and each subject is expected to contribute up to 2 observations. The study will be considered successful if $\geq 80\%$ of attempted FSO are dilated successfully with no USADE related to the UP Drug-Coated Device. A successful FSO dilation is defined as insertion of the UP Drug-Coated Device into the targeted FSO followed by 2 consecutive complete inflations.

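### SAP 7.1.1 judges the PK cohort's dilation-success rule on a population that already requires one successful dilation

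*SAP*

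**What the plan says.** SAP 7.1.1 limits the PK-cohort safety population to subjects and sinuses "exposed to the investigational device with successful dilation of at least one FSO". It then assigns the analyses: "All primary and secondary endpoint analyses will be performed on the safety population for the PK cohort". This is the only sentence in the SAP that names a population for the PK primary analysis.

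The endpoint and its pass rule are written on a different base:

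- SAP 6.1: "The primary endpoint in the PK cohort is the successful balloon dilation of attempted FSO using the UP Drug-Coated Device". The definition also rules out any unanticipated serious adverse device effect (USADE).
- SAP 10.3.1: "The primary endpoint is the number of successful sinus dilations of all attempted FSO using the UP Drug-Coated Device". The pass rule there is at least 80% of attempted FSO, with no related USADE.
- Protocol 9.2.1 defines the endpoint on attempted FSO, and Protocol 16.3 sets the rule at 80% or more "of attempted FSO are dilated successfully with no USADE related to the investigation device".

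Protocol 16.8 defines the safety population in the same way as the SAP but does not assign the primary endpoint to it. An attempt is defined only for the randomized cohort's intent-to-treat population (Protocol 3 and 16.8).

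**The concern.** The endpoint is whether dilation succeeds. A population that requires a success conditions the endpoint on its own outcome. A subject with two failed attempts contributes no successes and two failures. Under SAP 7.1.1 that subject leaves the analysis, and both failures go too. The same subject also leaves the population on which the no-USADE condition is judged.

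The same data could therefore pass under SAP 10.3.1's definition and fail under it only when 7.1.1 is set aside, or the reverse reading could be argued after the fact; the one constant is that using 7.1.1 helps the device. SAP 10.3.1 attaches a formal declaration of success to the 80% rule, and SAP 9.2 lets each cohort's result stand on its own, so the denominator should not be open to choice.

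**Working it through.** The documents give no computed figure to reproduce: the cohort size of 5 was not statistically derived, and 80% is a fixed criterion. The check is an exact enumeration.

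**Inputs from the documents.** 5 subjects (SAP 9.4.1); up to 2 FSO per subject, treated as independent: "The left and right sides of each subject will be considered independent, and each subject is expected to contribute up to 2 observations" (SAP 10.3.1); pass if at least 80% (SAP 10.3.1, Protocol 16.3).

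**Assumptions.** Both sides are attempted in every subject (10 FSO), and no subject is replaced. True success rates and within-subject correlation are not in the documents, so a range is shown.

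**Formulas.** Let n0, n1 and n2 be the numbers of subjects with 0, 1 and 2 successes, with n0 + n1 + n2 = 5.

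- Attempted FSO: (n1 + 2·n2) / 10, so a pass needs at least 8 successes.
- Safety population, subject level: (n1 + 2·n2) / (10 − 2·n0).

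The numerator is the same and the second denominator is never larger, so the rate cannot fall.

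**Enumeration.** There are 21 patterns, of which 15 have n0 ≥ 1. Among those 15:

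| n0, n1, n2 | Attempted FSO | Safety population | Verdict |
|---|---|---|---|
| 1, 1, 3 | 7/10 = 70% | 7/8 = 87.5% | fail to pass |
| 2, 0, 3 | 6/10 = 60% | 6/6 = 100% | fail to pass |
| 2, 1, 2 | 5/10 = 50% | 5/6 = 83.3% | fail to pass |
| 3, 0, 2 | 4/10 = 40% | 4/4 = 100% | fail to pass |
| 4, 0, 1 | 2/10 = 20% | 2/2 = 100% | fail to pass |
| 1, 0, 4 | 8/10 = 80% | 8/8 = 100% | pass either way |
| 5, 0, 0 | 0/10 = 0% | 0/0 | undefined, not counted as a pass |

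The other 8 patterns fail either way. No pattern moves from pass to fail. In this setting a changed verdict needs one bilateral failure plus at least one further failed FSO.

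**Probabilities.** For true rate p and within-subject correlation r, a subject has 2 successes with probability P2 = p² + r·p(1−p), 1 with P1 = 2p(1−p)(1−r), and 0 with P0 = 1 − P1 − P2. Pattern probabilities are multinomial. Example at p = 0.8, r = 0: P2 = 0.64, P1 = 0.32, P0 = 0.04, and pattern (1, 1, 3) has probability 5!/(1!·1!·3!) × 0.04 × 0.32 × 0.64³ = 20 × 0.04 × 0.32 × 0.2621 = 0.0671.

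Chance of meeting the 80% part (gaps taken before rounding):

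| p | r | Attempted FSO | Safety population | Gap (points) |
|---|---|---|---|---|
| 0.80 | 0 | 67.78% | 75.57% | 7.79 |
| 0.90 | 0 | 92.98% | 94.98% | 2.00 |
| 0.95 | 0 | 98.85% | 99.20% | 0.36 |
| 0.80 | 0.5 | 66.53% | 90.79% | 24.26 |
| 0.90 | 0.5 | 89.50% | 98.30% | 8.80 |
| 0.95 | 0.5 | 97.11% | 99.74% | 2.63 |

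At r = 0 the attempted-FSO column agrees with the binomial tail for 8 or more of 10 (0.6778 at p = 0.8, 0.9298 at p = 0.9). The single pattern 7/10 to 7/8 supplies 6.71, 1.91 and 0.35 points of the three independent-sides gaps. The chance of at least one bilateral failure at r = 0 is 18.5%, 4.9% and 1.2%.

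**Replacement.** The documents do not say whether a subject with no success is replaced. If enrolment continued until 5 subjects had at least one success, the r = 0 gaps would be 12.44, 2.94 and 0.49 points, again only toward success.

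**The case against.** The strongest reply is that the pass rule already carries its own denominator. Attempted FSO appears in two protocol sections and two SAP sections, including inside the rule itself, while 7.1.1 is one general sentence covering every PK analysis. A programmer working from SAP 10.3.1 would probably use attempted FSO, so this may be a drafting slip. That stands as a likely explanation, but it does not remove the conflict: 7.1.1 expressly covers all primary analyses, and following it would be compliant with the SAP.

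It is also fair that little depends on the result. The cohort is small and descriptive, with no hypothesis test. Access to each FSO must be confirmed beforehand, and inability to confirm it is a screen failure (Protocol 11.1), which makes the higher success rates, and so the smaller gaps, more plausible. The disposition summary (SAP 10.1) and the adverse event listings (SAP 10.7) would still show the dropped failures and events. All of this limits the weight of the point. None of those outputs decides the pass rule, however. The 24-point gap does rest on a correlation that the documents do not assume.

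Two further objections concern the enumeration. A subject whose first side fails and whose second is never attempted would also be dropped, turning 7/9 (77.8%) into 7/8 (87.5%). And the SAP definition speaks of sinuses as well as subjects: read per sinus, failed sides vanish and the rate is 100% by construction. Both are correct, and both make the bias larger.

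Last, the PK cohort enrols first, and SAP 9.2 claims a priori status only for the randomized analyses, so an amendment may not pre-specify anything for this cohort. The documents do not settle that. The inconsistency still has to be resolved before the result is reported.

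**Conclusion.** The concern holds. SAP 7.1.1 as written puts a dilation-success endpoint on a population selected for dilation success, against the endpoint definitions in both documents, and nothing says which prevails. The error runs only toward success: 5 of the 15 patterns with a bilateral failure change from fail to pass, and none the reverse. The practical size is modest, at 7.8, 2.0 or 0.4 percentage points in the chance of passing for true rates of 0.8, 0.9 or 0.95. Those figures assume 5 subjects, 10 attempted FSO, independent sides and no replacement; positive within-subject correlation would enlarge them. The consequence is confined to the PK cohort's pass rule. The randomized cohort is analysed by intent to treat and is unaffected. It should be fixed because it bears on a stated primary success criterion and the correction is simple.

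**What to change.** Amend SAP 7.1.1 to state that the PK-cohort primary endpoint, both dilation success and the USADE condition, is analysed on all PK-cohort subjects and FSO in which dilation with the UP Drug-Coated Device was attempted.

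Define an attempt for this cohort, since neither document does. The Protocol 16.8 wording can be used ("An attempt occurs when the physician introduces the UP Device into the subject's nostril with the intent of dilation"), applied separately to each targeted FSO, because nostril entry alone does not identify which FSO was attempted. The definition in SAP 7.2.1 should not be borrowed, as it is written for a treatment side and a control side. Keep the safety population for the secondary endpoints and the Protocol 16.8 PK population for the plasma concentration summaries. If PK outcomes are already known when the change is made, the amendment should say so.

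The cost is one amended sentence and one definition. No new data and no protocol amendment are needed. The only downside is that the reported success rate may be less favourable.

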7.2 Randomized Cohort

7.2.1 Intent-to-Treat Population

The intent-to-treat (ITT) population will consist of all subjects in whom the UP Drug-Coated Device or the UP Control Device was attempted. An attempt occurs when the surgeon introduces the UP Drug-Coated Device into the subject's nostril on the treatment side or the UP Control Device on the control side. Sinus sides will be analyzed according to their randomization assignment.

The ITT population is considered the principal analysis population. All primary and secondary efficacy endpoint analyses will be performed using the ITT population. Summaries for demographics, baseline clinical characteristics, procedure characteristics, procedure success, concomitant medication use, adverse events (AE), and study visit compliance will be carried out using the ITT population.

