Patency grading scale for the FSO	
Patency of the FSO assessed endoscopically by probing with a 3-mm olive-shaped frontal sinus suction tip ("suction tip") and graded on a 5-point scale as follows:
 
 0: Occluded (no opening visible) 1: Significantly stenosed (not occluded, but unable to pass the 3-mm suction tip) 2: Moderately stenosed (able to easily pass the 3-mm suction tip with no additional space around it) 3: Minimally stenosed (able to easily pass the 3-mm suction tip with additional 1-2 mm space around it) 4: Completely patent (able to easily pass the 3-mm suction tip with additional > 2 mm space around it)
Per-treatment-evaluable (PTE) population	Consists of all randomized patients who have received the assigned study device in the target sinus, who have no major procedural protocol deviations and for whom follow-up data are available.

Term	Definition
Polyp grading scale for the ethmoid sinus	
Polyps originating from the ethmoid sinus assessed endoscopically and graded on an 8-point scale ranging from 0 to 4 as follows:
 
 0: No visible sinonal polyps 1: Small amount of sinonal polyps confined in middle meatus 1.5: Small amount of sinonal polyps confined in middle meatus with expanded amount of polypoid edema obstructing $\geq 25\%$ of the ethmoid sinus cavity 2: Expanded amount of sinonal polyps confined in middle meatus 2.5: Expanded amount of sinonal polyps confined in middle meatus with expanded amount of polypoid edema obstructing $\geq 50\%$ of the ethmoid sinus cavity 3: Sinonal polyps extending beyond middle meatus but not totally obstructing the nasal cavity 3.5: Sinonal polyps extending beyond middle meatus with expanded amount of polypoid edema obstructing $\geq 75\%$ of the ethmoid sinus cavity 4: Sinonal polyps completely obstructing the nasal cavity
Polypoid edema grading scale for the FSO	
Polypoid edema in the frontal recess/FSO is assessed on a 4-point scale as follows:
 
 0: Normal mucosa, no visible polyps/mucosal edema 1: Minimal amount of polyps/mucosal edema 2: Moderate amount of polyps/polypoid edema 3: Expanded amount of polyps/polypoid edema
Safety population	
Consists of all subjects exposed to investigational device with successful dilation of at least one FSO

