7.2.2 Per-Treatment Evaluable Population

The per-treatment evaluable (PTE) population will consist of all subjects and sinuses that were successfully treated with the UP Drug-Coated Device on the treatment side and with the UP Control Device on the control side, have had no major procedural protocol deviations (i.e., if a study subject was treated before signing an ICF, or sinuses received a treatment not consistent with the randomization assignment), and have follow-up data available. Reasons for exclusion from PTE will be provided in data listings.

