10.7 Safety Measures

In the PK cohort, continuous data from the plasma MF, plasma cortisol and 24-hour urinary cortisol concentrations will be expressed using descriptive statistics, including but not limited to, mean, SD, medians, ranges and, where appropriate, coefficient of variation as described in [Section 9.3.1](#).

Adverse events will be coded using the Medical Dictionary for Regulatory Activities (MedDRA). Where possible, and if applicable, AE will be localized to a sinus type and side. If a subject reports the same AE more than once or experiences the same AE on multiple occasions, the maximum severity grade and relationship to the study drug, study device, accessory devices, and/or dilation procedure will be presented.

The incidence and percentages of AE and serious adverse events (SAE) through Day 30 in the PK cohort and through Day 60 in the randomized cohort, including adverse device effects and USADE, will be presented by MedDRA system organ class (SOC) and preferred term (PT). Complete subject listings of all AE will be provided. For each AE, the following will be specified:

- Start and stop dates, and event onset (study day)
- The affected side (right or left) if available
- Seriousness
- Severity
- Strength of relationship
- Action taken
- Outcome

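### No rule assigns side-localised adverse events in the randomized cohort to the device actually received, so any summary split by treatment and control side would misplace a swapped subject's events

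*SAP*

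**What the plan says.** For the randomized cohort, SAP 7.2 defines two populations, ITT and PTE. SAP 7.2.1 ends its definition of ITT with "Sinus sides will be analyzed according to their randomization assignment". Its next paragraph makes ITT the principal population for efficacy and also assigns several descriptive summaries to it: "concomitant medication use, adverse events (AE), and study visit compliance will be carried out using the ITT population". Protocol 16.8 has the same rule for ITT: "Subjects and sinuses will be analyzed according to randomization assignment".

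SAP 7.2.2 lists, among the major procedural deviations that exclude data from PTE, the case where "sinuses received a treatment not consistent with the randomization assignment". No adverse event summary on PTE is planned.

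The SAP's exposure-based set is defined in 7.1.1, under the PK cohort: "The safety population will consist of all subjects and sinuses exposed to the investigational device with successful dilation of at least one FSO". Protocol 16.8 also places its safety population under the PK cohort. The Protocol glossary entry is not tied to a cohort ("Consists of all subjects exposed to investigational device with successful dilation of at least one FSO"), but it decides who is included. It does not say under which device a side is counted.

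On side, SAP 10.7 says: "Where possible, and if applicable, AE will be localized to a sinus type and side". It presents incidence by system organ class and preferred term, and the listing carries the anatomical side where available.

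**The concern.** Efficacy is properly analysed as randomised. For safety, the usual question is what happened to tissue exposed to a given product, and that calls for assignment by actual exposure. SAP 7.2.1 applies one rule to both.

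The design makes this more than a formality. Each subject is planned to receive the drug-coated device on one side and the control device on the other, so subject-level counts cannot separate the two. The within-subject safety contrast comes only from events that can be placed on one side. Some risks listed in Protocol 15.1 can be one-sided, such as injury to the orbital wall, swelling or infection around the eye, and nosebleed.

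A swap is conceivable: under Protocol 17.3.2 the operator matches two coded devices to two sides from an envelope, and the SAP names the resulting deviation. Under the as-randomised rule, an event on the drug-exposed side of a swapped subject would appear under control, and the reverse.

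**Working it through.** **Step 1: is there a rule by device received?** Taking the places where one could stand:

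- SAP 7.2.1 and Protocol 16.8 (ITT): sides follow randomization.
- SAP 7.2.2 (PTE): sinuses treated against assignment are removed, and no adverse event summary uses this set.
- SAP 7.1.1 and Protocol 16.8 (safety population): placed under the PK cohort.
- Protocol 3 (glossary): exposure decides inclusion, with no rule for labelling sides.
- SAP 10.7: events are localised to a side where possible, with no statement on device received.

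No such rule exists for adverse events in the randomized cohort.

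**Step 2: what would a swap do to a summary split by side?** The plan states no figure for this. The one plan input is the cohort size, 53 + 17 = 70 (SAP 9.4.2). The number of swaps and the event rates are assumptions.

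Let s of the 70 subjects have both sides swapped, let f = s/70, and let pT and pC be the true rates of a side-localised event on drug-exposed and control-exposed sides. Assume swaps are unrelated to event risk. The expected rates by randomised side are then:

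- treatment column: (1 − f)·pT + f·pC
- control column: (1 − f)·pC + f·pT
- difference: (1 − 2f)·(pT − pC)

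Each full swap therefore removes 2/70 = 2.9% of the true difference. With assumed rates of 0.10 and 0.05 (true difference 0.050), the expected number of misplaced events is s × (0.10 + 0.05):

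| Swaps (assumed) | Factor 1 − 2s/70 | Expected difference | Expected events misplaced |
|---|---|---|---|
| 0 | 1.000 | 0.0500 | 0 |
| 1 | 0.971 | 0.0486 | 0.15 |
| 3 | 0.914 | 0.0457 | 0.45 |
| 7 | 0.800 | 0.0400 | 1.05 |

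The factor does not depend on the rates. With sides labelled by device received it is 1.000 whatever the number of swaps.

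**Step 3: a single rare event.** Suppose one side-specific serious event occurs in the cohort, independently of swapping. The chance that it falls in a swapped subject is s/70: 1/70 = 1.4%, 2/70 = 2.9% and 4/70 = 5.7% for 1, 2 and 4 assumed swaps. Otherwise it is placed correctly.

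**Step 4: what does not move.** A full swap leaves the subject exposed to both devices, so subject-level incidence, serious event counts and systemic events are the same under either rule. The sample size rests on patency grade and does not change.

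**The case against.** The strongest objection is that the SAP never says adverse events are tabulated by randomised side. SAP 10.7 describes incidence by system organ class and preferred term, the listing field is right or left rather than treatment or control, no side-to-side test of adverse events is planned, and the table mock-ups show only headings in the available text. This stands. A reader who joins SAP 7.2.1 to the localisation rule in 10.7 might infer a planned treatment-versus-control table, but the documents do not state one. The point is therefore conditional on such a split being made.

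Three further arguments narrow it:

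- Few events are exposed to the problem. Protocol 14.1 keeps scarring, polyp formation, restenosis and the need for intervention in the ostium out of the adverse event definition. What remains is events that are both localised and one-sided.
- Causality is rated separately by the investigator against drug, investigational device, accessory device and procedure (SAP 6.3.2), so formal relatedness does not depend on the side label.
- A swap would be visible. Major deviations enter the disposition outputs (SAP 10.1), reasons for PTE exclusion are listed (SAP 7.2.2), and the event listing shows the side. A reader could trace a misplaced event by hand, although this does not correct a summary table.

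None of these supplies the missing rule. The one labelling rule that the plan does state would give the wrong answer for a deviation that the plan itself names.

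**Conclusion.** The concern holds in a limited form. If adverse events in the randomized cohort are summarised by treatment and control side under SAP 7.2.1, a swapped subject's side-localised events would be credited to the wrong device.

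The expected size is small, at 2.9% of the true side-to-side difference per full swap among 70 subjects. This assumes that both sides are swapped and that swaps are unrelated to event risk. The documents give no swap count and nothing to suggest that swaps are common. With no swaps, the two rules give identical results.

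Two stronger readings are not supported. A reader might infer that one swap reverses the comparison for a rare serious event. That requires the event to occur in the swapped subject, a 1.4% chance for one swap and one unrelated event. A reader might also extend the point to device malfunctions, but SAP 7.2.1 does not list them among the ITT summaries, and no passage assigns them by randomised side.

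**What to change.** Add one sentence to SAP 7.2.1 and a matching one to 10.7: in the randomized cohort, adverse events localised to a side are summarised by the device actually received on that side. Keep assignment by randomization for the efficacy analyses.

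The cost is two sentences before database lock. The device used on each side must already be known to decide PTE membership. Sample size, efficacy analyses and subject-level safety counts do not change.
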